### ***Disease characteristics at baseline***

Specific disease characteristics include:

- Type of hypercholesterolemia
  - Heterozygous familial hypercholesterolemia (heFH): patients included in the groups A, B or C and some patients in the group E, at entry in the study (See [Section 1.1](#) ),
  - Non-familial hypercholesterolemia (non-FH): patients included in the group D and some patients in the group E, at entry in the study (See [Section 1.1](#) ).
- For heFH patients
  - Time from diagnosis of hypercholesterolemia (years) computed as:  
(Year of inclusion - year of diagnosis) + (Month of inclusion - month of diagnosis)/12  
Confirmation of diagnosis (genotyping (Yes, No), WHO/Simon Broome criteria).
- For non-FH patients
  - Time from diagnosis of hypercholesterolemia (years) computed as:  
(Year of inclusion - year of diagnosis) + (Month of inclusion - month of diagnosis)/12.
- Lipid modifying therapy history, as reported in the “History of Hyperlipoproteinemia” eCRF page:
  - Type of lipid-modifying therapy ever taken (hydroxymethylglutaryl-coenzyme A [HMG CoA] reductases inhibitors [statin], fibrates, bile acid sequestrant, cholesterol absorption inhibitor, nicotin acid and derivatives, omega 3 fatty acid  $\geq 1000$  mg/day, other),
  - Number of patients taking at screening high intensity statins (atorvastatin 40 to 80 mg, rosuvastatin 20 to 40 mg or simvastatin 80 mg) daily and, for those not taking one of these agents at one of the specified doses, reasons for being on a lower dose or for not taking a statin ,
  - Number of patients receiving Simvastatin 80 mg/daily for at least 12 months without myopathy,
  - Number of patients with history of down titration of any statin dose due to tolerability issue,
  - Number of patients with history of change to any different statin due to tolerability issue.

### ***Drug utilization: starting dose of alirocumab***

The starting dose of alirocumab dispensed by investigator at inclusion will be described (75 mg or 150 mg) as well as who performed the first injection (patient, designated person, site member). It will be checked that any patient who self-injected or any designated person who injected the patient performed the training injection (with placebo).

### ***Other baseline characteristics***

Other baseline characteristics include:

- Body mass index (BMI) in kg/m^2 (quantitative and qualitative variable: <30, ≥30)
- Smoking status (Never smoked, Quit smoking, Currently smoker)
- Alcohol habits (Never, Occasionally, at least monthly, at least weekly, at least daily)
- Weight (quantitative and qualitative variable: <50, ≥50 to <70, ≥70 to <100 and ≥100 kg).
- Height (cm)
- Glycated hemoglobin A1c (HbA1c) (quantitative and qualitative variable: <5.7%, ≥5.7% to <6.5%, ≥6.5%)
- Efficacy lipid parameters - Quantitative analysis for all efficacy parameters, including Total-C and non-HDL-C, and the following qualitative categories for LDL-C, HDL-C, non HDL-C and TG:
  - Calculated LDL-C: <70, [70-100[, ≥100 to <130, ≥130 to <160, ≥160 to <190, ≥190 mg/dL, ie, <1.81, ≥1.81 to <2.59, ≥2.59 to <3.37, ≥3.37 to <4.14, ≥4.14 to <4.91, ≥4.91 mmol/L
  - HDL-C: <40, ≥40 mg/dL, ie, <1.04, ≥1.04 mmol/L
  - TG: <150, ≥150 to <200, ≥200 mg/dL, category ≥150 mg/dL (mixed dyslipidemia) will be also displayed, ie, <1.7, ≥1.7 to <2.3, ≥2.3 mmol/L
  - Non HDL-C: <100, [100-130[, [130-160[, [160-190[, [190-220[, ≥220 mg/dL, ie, <2.59, [2.59-3.37[, [3.37-4.14[, [4.14-4.91[, [4.91-5.7[, ≥5.7 mmol/L

Any technical details related to computation, dates, and imputation for missing dates are described in [Section 2.5](#).

#### **2.1.2 Prior or concomitant medications**

All medications started within 12 weeks before screening visit and until the end of the study include:

- Lipid modifying therapies (including statins)
- Cardiovascular drugs
- Other

All medications will be coded using the World Health Organization-Drug Dictionary (WHO-DD) using the version currently in effect at Sanofi at the time of database lock.

- Prior medications are those the patient used within 12 weeks prior to screening visit and prior to the first injection of alirocumab. Prior medications can be discontinued before first administration or can be ongoing during treatment phase.
- Concomitant medications are any treatments received by the patient concomitantly with alirocumab, from the first injection of alirocumab up to the last injection +2 weeks. Any given medication can be classified both as a prior medication and as a concomitant medication depending on the timing of administration.
- Post-treatment medications are those used beyond 2 weeks after the last injection up to the end of study.

For medications classified as “LMT”, a flag will be created to categorize “Statin” and “other LMTs”.

All medications with the following anatomical therapeutic chemical (ATC) codes will be described and considered as **Statin**:

- C10AA, C10BA, and C10BX.

All medications with the following ATC codes will be described and considered as **other LMTs**:

- C10AX06 (Omega-3-triglycerides), C10AX09 (Ezetimibe), C10AD02 (Nicotinic acid), C10AC01 (Colestyramine); C10AC02 (Colestipol); C10AC04 (Colesevelam); C10AB05 (Fenofibrate) and any other (for the rest).

Any technical details related to computation, dates, imputation for missing dates are described in [Section 2.5](#).

### 2.1.3 Efficacy endpoints

Efficacy endpoints include lipid parameters: calculated LDL-C, Total-C, HDL-C, TG, non-HDL-C. Total-C, HDL-C, TG will be provided by a local Laboratory. LDL-C will be calculated using the Friedewald formula [\(1\)](#) at all site visits (see [Section 2.5.1](#)). One of the most important limitations of the Friedewald formula is that it is not appropriate at TG concentrations >400 mg/dL, anyway and in order to simplify the computations this formula will be used regardless of the TG values. Non-HDL-C is calculated by subtracting HDL-C from the Total-C.

Unless otherwise specified, all lipid values (scheduled or unscheduled, fasting or not fasting) may be used to provide a value for the efficacy endpoints. All measurements, scheduled or unscheduled, fasting or not fasting, will be assigned to analysis windows defined in [Table 2](#) in order to provide an assessment from Week 4 to the end of the study.

The main efficacy endpoint will be the LDL-C at Week 12 (change from baseline). Nevertheless, all efficacy endpoints will be described at each time point.

For all post-baseline time points, the value used for the analyses at a given time point will be the value obtained within the corresponding analysis window. The baseline value is defined as the last available measurement obtained before the date of the first injection of alirocumab.

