E 12. New cancer or active progression of cancer within the past 5 years, except for adequately treated basal cell skin cancer, squamous cell skin cancer, or in situ cervical cancer.

E 13. Known history of a positive HIV test.

E 14. Patient who has taken any active investigational drugs with the exception of alirocumab within 1 month or 5 half-lives, whichever is longer.

NB: Patients who received an investigational drug before 1 month or 5 half-lives (whichever is longer) and who fulfill all the other selection criteria can be enrolled but only after the formal approval from the Sponsor.

E 15. Known history of homozygous familial hypercholesterolemia.

E 16. Use of continuous hormone replacement therapy unless the regimen has been stable in the past 6 weeks prior to the Screening visit (Week-3) and no plans to change the regimen during the study.

E 17. Patient who withdraws consent during the screening period (patient who is not willing to continue or fails to return).

E 18. Any clinically significant abnormality identified at the time of screening that in the judgment of the Investigator or any sub-Investigator would preclude safe completion of the study or constrain endpoints assessment such as major systemic diseases, patients with short life expectancy.

E 19. Patients considered by the Investigator or any sub-Investigator as inappropriate for this study for any reason, eg:

- Those deemed unable to meet specific protocol requirements, such as scheduled visits,
- Those deemed unable to administer or tolerate long-term injections as per the patient or the investigator,
- Investigator or any Sub-Investigator, pharmacist, study coordinator, other study staff or relative thereof directly involved in the conduct of the protocol, etc,
- Presence of any other conditions (eg, geographic, social) actual or anticipated, that the Investigator feels would restrict or limit the patient’s participation for the duration of the study.

E 20. Laboratory findings during the screening period:

- Positive test for Hepatitis B surface antigen or Hepatitis C antibody,
- Positive serum or urine pregnancy (including Week 0) test in women of childbearing potential,
- Triglycerides >400 mg/dL (>4.52 mmol/L) (1 repeat lab is allowed),
- Estimated glomerular filtration rate (eGFR) <30 mL/min/1.73 m^2 according to 4-variable modification of diet in renal disease (MDRD) Study equation,

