**Table 2 - Protocol amendment statistical changes**

Amendment Number	Date Approved	Rationale	Description of statistical changes
Clinical Trial Amendment no. 5 (ie, the first global protocol amendment)	01Mar2016	
Reassessment of the number of patients planned to be enrolled from 1100 initially planned to 1300
 
Streamlining of the requirements for the end of study
 
Standardization across the protocols for observational studies
 
Clarification regarding the LDL-C assessment given that efficacy is a secondary endpoint and that no central lab is utilized in this study
 
Although there is no formal interim analysis, some statistical analyses might be performed before the end of the study in order to support a dossier of reimbursement if required by health authorities in some countries
	
Modifications of the table of expected 95% CI for various adverse events rates
 
Only one final on-site visit called “EOT/EOS Visit” is required
 
Modification of the list of the AE of special interest
 
The Friedewald formula to assess LDL-C will be used even in case TG is elevated (>400 mg/dL)
 
Some statistical analyses might be performed before the end of the study

In addition to the medical history of specific interest to be described such as quoted in the protocol (CHD, CHD risk equivalents...), the multiple manifestations of CV disease (see [Section 2.1.1](#)) was added due to the very high risk of CV event profile of patients enrolled in this study.

Some secondary efficacy analyses were added compared to the original version of the protocol, mainly regarding the occurrence of very low LDL-C level and the associated changes in treatment (see [Section 2.4.4.4](#)) in order to better characterize these cases.

Additional descriptive analyses were added to document the adherence to statins according to alirocumab dose and the achieved LDL-C.

Two subgroups that are of particular clinical interest due to the very high risk of CV event profile of these patients were added, namely primary CVD prevention and the subgroup of patients with multiple manifestations of CV diseases.

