#### **2.4.4.4 Additional efficacy analyses**

##### ***Occurrence of very low LDL-C level***

A LDL-C level <25 mg/dL (0.65 mmol/L) will be defined as very low. An alternative definition with a cut-off at 15 mg/dL (0.39 mmol/L) will also be used.

For each definition of very low LDL-C level, the number and percentage of patients who had a very low LDL-C level at least once during the observational period will be provided overall, by the LDL-C level at baseline (<70 mg/dL (1.81 mmol/L),  $\geq 70$  mg/dL and <100 mg/dL (2.59 mmol/L),  $\geq 100$  mg/dL and <130 mg/dL (3.37 mmol/L),  $\geq 130$  mg/dL and <160 mg/dL (4.14 mmol/L),  $\geq 160$  mg/dL) and by starting dose of alirocumab.

Among patients with a very low LDL-C level, the number and percentage of patients receiving each level of dose for alirocumab (75 mg and 150 mg) at the time of the corresponding LDL-C test will be provided. The time from the first injection of Alirocumab to the first occurrence of a very low value of LDL-C will also be displayed.

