### ***Change in study treatment after the occurrence of very low LDL-C level***

For each definition of very low LDL-C level, the following statistics will be calculated:

- Among the patients who had a very low LDL-C level and received a dose of alirocumab at 150 mg at the time of the corresponding LDL-C test:
  - Number and percentage of patients for whom the dose of alirocumab was changed to 75 mg, at least once at any time after the first occurrence of a very low LDL-C level,
  - Number and percentage of patients for whom alirocumab was discontinued at any time after the first occurrence of a very low LDL-C level,
  - Number and percentage of patients for whom the doses of other lipid-lowering drugs were decreased at any time after the first occurrence of a very low LDL-C level,
  - Number and percentage of patients for whom other lipid-lowering drugs were discontinued at any time after the first occurrence of a very low LDL-C level.
- Among the patients who have a very low LDL-C level and received a dose of alirocumab at 75 mg at the time of the corresponding LDL-C test:
  - Number and percentage of patients for whom alirocumab was discontinued at any time after the first occurrence of a very low LDL-C level,
  - Number and percentage of patients for whom the doses of other lipid-lowering drugs were decreased at any time after the first occurrence of a very low LDL-C level,
  - Number and percentage of patients for whom other lipid-lowering drugs were discontinued at any time after the first occurrence of a very low LDL-C level.

For patients who experienced a very low LDL-C several times during the observational period, only the first occurrence will be considered.

The 95% CI will be provided. In case of a number of patients deemed insufficient, the Clopper-Pearson algorithm will be used to compute the 95% CI.

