### ***Discontinuation of alirocumab***

The following statistics will be calculated:

- Number and percentage of patients for whom alirocumab is discontinued during the observational period
  - Overall,
  - By starting dose of alirocumab.
- Among the patients for whom alirocumab is discontinued
  - Number and percentage of patients on each dose (75 versus 150 mg) prior to discontinuation,
  - Number and percentage of patients who had LDL-C <25 mg/dL (0.65 mmol/L) and <15 mg/dL (0.39 mmol/L) prior to discontinuation, respectively,

- Number and percentage of patients according to each reason for discontinuation, if available,
- Number and percentage of patients who restarted alirocumab in the observational period.

For patients who discontinued alirocumab several times during the observational period, only the first occurrence will be considered.

The 95% CI will be provided. In case of a number of patients deemed insufficient, the Clopper-Pearson algorithm will be used to compute the 95% CI.

In addition, a listing with all patients who experienced at least once a very low LDL-C level during the observational period will be provided with the following parameters: country, date of enrollment, starting dose of alirocumab, LDL-C level at inclusion, LDL-C <25 mg/dL (Y/N), LDL-C <15 mg/dL (Y/N), date corresponding to the lipid test, down-titration (Y/N), date of down-titration, up-titration (Y/N), date of up-titration, discontinuation of alirocumab (Y/N), date of discontinuation.

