### ***Lipid formulas***

**LDL-C** is calculated using the Friedewald formula (1) in all cases, ie, even in case TG are elevated (>400 mg/dL):

- $\text{LDL-C} = \text{Total-C} - \text{HDL-C} - (\text{TG}/2.17)$ , when all concentrations are expressed in mmol/L.
- $\text{LDL-C} = \text{Total-C} - \text{HDL-C} - (\text{TG}/5)$ , when all concentrations are expressed in mg/dL.  
In order to convert the result into mmol/L, divide by 39.

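### LDL-C calculated by Friedewald at TG >400 mg/dL enters the single-value very-low-LDL-C tables with no flag and no analysis without those values

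*SAP*

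**What the plan says.** **The formula.** SAP 2.1.3 names the limitation and sets it aside in one sentence: "it is not appropriate at TG concentrations >400 mg/dL, anyway and in order to simplify the computations this formula will be used". SAP 2.5.1 (Lipid formulas) repeats that LDL-C "is calculated using the Friedewald formula (1) in all cases, ie, even in case TG are elevated (>400 mg/dL"). SAP 1.5, Table 2, records it as a change made with Amendment 5: "The Friedewald formula to assess LDL-C will be used even in case TG is elevated". The rationale given there is that efficacy is a secondary endpoint and that there is no central laboratory.

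**What limits exposure.** Exclusion E 20 in Protocol 7.2.1 removes patients with "Triglycerides >400 mg/dL (>4.52 mmol/L) (1 repeat lab is allowed") during screening. Protocol section 10 (Blood samplings) says that a patient who is not fasting is not sampled and is rebooked. SAP 2.1.3, however, accepts fasting and non-fasting values alike.

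**Where the values go.** SAP 2.4.4.4 defines very low LDL-C as <25 mg/dL, with <15 mg/dL as an alternative. It reports:

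- "the number and percentage of patients who had a very low LDL-C level at least once during the observational period";
- treatment changes afterwards, with this rule: "For patients who experienced a very low LDL-C several times during the observational period, only the first occurrence will be considered";
- among patients who discontinued, "Number and percentage of patients who had LDL-C <25 mg/dL (0.65 mmol/L) and <15 mg/dL (0.39 mmol/L) prior to discontinuation";
- statin reduction or discontinuation in patients with one or more values <25 mg/dL.

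The accompanying patient listing includes "LDL-C level at inclusion, LDL-C <25 mg/dL (Y/N), LDL-C <15 mg/dL (Y/N), date corresponding to the lipid test, down-titration (Y/N), date of down-titration", followed by up-titration and discontinuation fields. TG and non-HDL-C are not among its fields.

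**The concern.** The SAP declares the formula unsuitable in a defined range and then uses its results there without marking them. For a mean over many patients, a few such values would matter little. The very-low-LDL-C tables are different: a patient enters after one value at any visit, and that value sets the starting point for counting later dose changes and discontinuations. A reader of those tables or the listing could not tell a low LDL-C at ordinary TG from one produced by a large TG term.

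Protocol section 4 says that the safety of LDL-C below 25 mg/dL is still being assessed, so readers will look at how often such values occur. The stake is the readability of secondary, descriptive outputs.

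**Working it through.** **Inputs.** Formula: SAP 2.5.1. Cut-offs of 25 and 15 mg/dL: SAP 2.4.4.4. TG limit of 400 mg/dL = 4.52 mmol/L: E 20. TG criterion for a potentially clinically significant abnormality (PCSA), ≥4.6 mmol/L: SAP Appendix A. N = 1300: SAP 1.3. The plan gives no figure for how often TG exceeds 400 mg/dL on treatment, or for the Friedewald error, so there is no plan figure to reproduce on the main point.

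**Step 1: what the formula does at high TG.** In mg/dL, LDL-C = Total-C − HDL-C − TG/5 = non-HDL-C − TG/5. A sample reads <25 when non-HDL-C < 25 + TG/5, reads <15 when non-HDL-C < 15 + TG/5, and is negative when non-HDL-C < TG/5.

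| TG (mg/dL) | TG/5 | Reads <25 if non-HDL-C below | Reads <15 if below | Negative if below |
|---|---|---|---|---|
| 400 | 80 | 105 | 95 | 80 |
| 500 | 100 | 125 | 115 | 100 |
| 600 | 120 | 145 | 135 | 120 |

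The subtracted term is at least 80/25 = 3.2 times the cut-off. The table shows which samples would be classed as very low, not that the class is false. Only negative values are wrong on their face.

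**Step 2: opportunities.** Protocol section 10 schedules post-baseline lipid profiles at Weeks 4, 8, 12, 24, 48, 72, 96 and EOT/EOS. That is at most 8 per patient, and fewer when treatment ends early. One patient is 1/1300 = 0.08 percentage points.

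**Step 3: existing cross-checks.** The PCSA threshold is 4.6 × 400/4.52 = 407 mg/dL, close to 400. That listing is separate and marks the patient's TG, not the LDL-C value calculated from it.

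**Step 4: possible size, by assumption only.** Suppose 0.5% to 5% of 1300 patients (6.5 to 65) have a sample with TG >400 mg/dL. With the denominator fixed, removing flagged values cannot move the occurrence table by more than 0.5 to 5 points. If the formula also reads too low (an assumption), if 10% to 50% of these patients not truly very low are read as <25, and if the true rate is 10%, the added cases run from 1300 × 0.005 × 0.10 × 0.90 = 0.6 to 1300 × 0.05 × 0.50 × 0.90 = 29. The table would show 10.05% to 12.25%. For the Week 12 mean percent change, an assumed error of 15 to 60 mg/dL at an assumed baseline of 160 mg/dL gives a shift of 0.005 × 15/160 = 0.05 points to 0.05 × 60/160 = 1.9 points.

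**Step 5: the divisor (separate point).** SAP 2.5.1 converts mg/dL to mmol/L by dividing by 39.

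| mg/dL | SAP cut-off (mmol/L) | ÷ 39 | ÷ 38.67 |
|---|---|---|---|
| 70 | 1.81 | 1.795 | 1.810 |
| 100 | 2.59 | 2.564 | 2.586 |
| 25 | 0.65 | 0.641 | 0.646 |
| 15 | 0.39 | 0.385 | 0.388 |

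A result calculated in mg/dL, converted by 39 and classified in mmol/L therefore meets effective cuts of 1.81 × 39 = 70.6, 2.59 × 39 = 101.0, 0.65 × 39 = 25.4 and 0.39 × 39 = 15.2 mg/dL. Assume on-treatment LDL-C is normal with mean 70 to 90 and SD 35 to 45 mg/dL, and that every result crosses units. The proportions then shift by 0.48 to 0.68 points (<70), 0.60 to 0.93 (<100), 0.04 to 0.12 (<25) and 0.01 to 0.05 (<15). A narrower SD gives more near the mean: about 0.95 points at <70 for mean 70 and SD 25.

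**The case against.** The sponsor can fairly say that this was a considered simplification. The limitation is stated, the amendment gives a reason, no formal test is planned, and no efficacy endpoint is primary. Exposure may be small: E 20 and the fasting rule apply, and Protocol section 4 reports lower triglycerides with alirocumab. A questionable flag needs TG >400 mg/dL and a fairly low non-HDL-C in the same sample. Non-HDL-C, which has no TG term, is reported at Week 12 and over time, and SAP 2.5.3 drops values that the laboratory marks invalid, although that rule sits under PCSA handling.

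All of this stands, and it rules out two stronger readings. A reader might infer that the very-low-LDL-C counts will be inflated. The documents call the formula not appropriate above 400 mg/dL but do not say that it reads too low, by how much, or how often it would apply. A reader might also infer that the safety conclusions are compromised. The tables sit under additional efficacy analyses, and no planned table compares adverse events by very-low-LDL-C status.

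Nor does it count against the SAP that background figures in Protocol section 4 use 2 consecutive values <25 mg/dL. Those are other trials' conventions, and a first single value is a reasonable anchor for describing what followed.

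The objection does not remove the gap: none of these safeguards identifies the affected LDL-C values or shows the tables without them.

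**Conclusion.** The point holds as a reporting gap. The SAP uses a formula in a range where it calls it not appropriate, lets one resulting value classify a patient as very low, and provides neither a flag nor a with/without display. The arithmetic in Step 1 is exact. The size of the effect is unknown: the ranges in Step 4 rest entirely on assumed frequencies and an assumed downward error, and the true effect could be negligible. That uncertainty is the reason to show the data both ways. The outputs concerned are secondary and descriptive.

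The divisor is a real but minor mismatch. It touches only results calculated in one unit and classified or reported in the other, and stays under 1 percentage point under the assumptions stated. SAP 2.5.1 also gives a direct mmol/L formula, which avoids it. Percent change and the ≥50% reduction criterion do not depend on it.

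**What to change.** 1. Flag every calculated LDL-C from a sample with TG >400 mg/dL (4.52 mmol/L).
2. Add TG and non-HDL-C to the very-low-LDL-C listing.
3. Show the SAP 2.4.4.4 very-low-LDL-C tables and the Week 12 LDL-C endpoints with and without flagged values. Keep all patients in the mITT population, delete no value, and leave the values available to investigators visible in the treatment-change table. If fasting status is recorded for lipid samples, values known to be non-fasting can be treated the same way. A count based on 2 consecutive values is optional.
4. Separately, use one conversion factor in both directions, such as 38.67, and classify in one stated unit. The SAP 2.1.1 pairs 130 mg/dL = 3.37 and HDL-C 40 mg/dL = 1.04 mmol/L then need aligning (130/38.67 = 3.362; 40/38.67 = 1.034).

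Cost: SAP wording, one derived flag, two listing columns and a few extra table rows. TG is already an input to the formula, so the flag needs no new data. If no sample is affected, a footnote can say so.
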